### 9.3.4 Immunogenicity Analysis

#### Primary Immunogenicity Endpoints:

- Evaluate the seroconversion rate of S-RBD IgG antibody on Day 28, Day 84, and Week 24 and Week 52 after vaccination, measured by ELISA.
- Evaluate the above-mentioned parameters comparing one versus two Ad5-nCoV doses.

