Objectives	
Primary Safety Objectives:
 

• Evaluate the incidence of solicited adverse reactions within 7 days after vaccination.

• Evaluate the incidence of unsolicited adverse events within 28 days after vaccination.

• Evaluate the HIV viral load 24 and 52 weeks after vaccination

• Evaluate the incidence of serious adverse events (SAE) and medically attended adverse events (MAE) within 52 weeks after vaccination in all participants.

 
Primary Immunogenicity Objectives:
 

• Evaluate the seroconversion rate of S-RBD IgG antibody on Day 28, Day 84 and Week 24 and Week 52 after vaccination, measured by ELISA.

• Evaluate the immunogenicity of two doses of the vaccine.

 
Secondary Safety Objectives:
 

• Evaluate the incidence of a decrease in CD4+ cell count by <math>\geq 20\%</math> at 24 and 52 weeks after vaccination.

• Evaluate changes in the CD4/CD8 ratio at 24 and 52 weeks compared to the basal value.

• To evaluate the efficacy of two doses of Ad5-nCoV in different age groups from 14 and 28 days to 24 and 52 weeks after vaccination. This will be evaluated by weekly participant contact to assess for any signs or symptoms of COVID 19.

 
Secondary Immunogenicity Objectives:
 

• Evaluate the GMT of S-RBD IgG antibody on Day 28, Day 84 and Week 24 and Week 52 after vaccination, measured by ELISA.

• Evaluate the GMI of S-RBD IgG antibody on Day 28, Day 84 and Week 24 and Week 52 after vaccination, measured by ELISA.

• Evaluate the seroconversion rate of pseudo-virus neutralizing antibody on Day 28, Day 84 and Week 24 and Week 52 after vaccination.

• Evaluate the GMT of pseudo-virus neutralizing antibody on Day 28, Day 84 and Week 24 and Week 52 after vaccination.

• Evaluate the GMI of pseudo-virus neutralizing antibody on Day 28, Day 84 and Week 24 and Week 52 after vaccination.

- Evaluate the positive rate and level of IFN- $\gamma$ , TNF, IL-4, IL-5, IL-13 stimulated by peptide pool of S protein on Day 28, Day 84 and Weeks 24 and Week 52 after vaccination, measured by intracellular cytokine staining (ICS) (in a subset of approximately 50 participants).

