Phase I trials found that the Ad5-vectored COVID-19 vaccine was tolerable in healthy adults [5]. The study was designed and carried out as a dose-escalation, single-centre, open-label, non-randomised clinical trial. 108 healthy adults participated in the phase I portion of the study and were divided into low, medium, and high-dose Ad5-nCoV vaccine groups. Participants received a dose on Injection visit. A total of 87% of participants reported at least 1 AE during the first 7 days after receiving the vaccine. The most common local AE was pain at the injection site, while fatigue, headache and fever were the most frequently reported systemic AE. Most reported AE were classified as mild to moderate and were self-limiting. However, there were 5 incidences of a Grade 3 fever in the high dose group. There was also higher occurrence of severe fever, fatigue, muscle pain, or joint pain, (which might be associated with viremia caused by Ad5 vector infection) in participants who received the of  $1.5 \times 10^{11}$  viral particles. For this reason, the low ( $5 \times 10^{10}$  vp per mL) and medium dose ( $1 \times 10^{11}$  vp per mL) were selected to progress to phase II trials. No SAE were recorded within 28 days of receiving the vaccine.

All three doses of the Ad5-nCoV vaccine demonstrated good immunogenicity in participants [5]. Anti-RBD antibodies were present in all groups after Day 14 and had at least a 4-fold increase in 97%, 94% and 100% of participants in the low, medium, and high doses respectively. Both ELISA and neutralizing antibodies increased significantly at 14 days post vaccination and peaked at 28 days post vaccination, in all three groups. A rapid T-cell response was observed in all groups by Day 14 as well.

On July 20th, 2020 the Phase II results of the Ad5-nCoV clinical trial were published. 508 healthy adults  $\geq 18$  years of age were randomized into three groups to receive Ad5-nCoV vaccine at either  $1 \times 10^{11}$  vp per mL or  $5 \times 10^{10}$  vp per mL, or a placebo vaccine in a 2:1:1 ratio, respectively [2]. The main objectives of this study were to assess the immunogenicity and safety of receiving the Ad5-nCoV vaccine, and to determine the appropriate dose to be administered for the efficacy study (currently, phase III).

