In its original version, the protocol limited inclusion to "people living with HIV on stable treatment and virologically suppressed..." .

Likewise, the design was double-blind versus placebo in a 2:1 ratio.

The advancement of the national vaccination reduced the possibilities of access to the study under such design, for which this protocol amendment was proposed.

Volunteers initially included in the study will receive two doses of the vaccine and will continue their follow-up as established in the protocol.

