## **2. STUDY OBJECTIVES**

### **2.1 Primary Objectives**

The primary objectives of the study are related to the safety and immunogenicity of the Ad5-nCoV in persons living with HIV.

There are four primary safety objectives.

1. Evaluate the incidence of solicited adverse reactions within 7 days after vaccination.
2. Evaluate the incidence of unsolicited adverse events within 28 days after vaccination.
3. Evaluate the HIV viral load 24 and 52 weeks after vaccination.
4. Evaluate the incidence of serious adverse events (SAE) and medically attended adverse events (MAE) within 52 weeks after vaccination in all participants.

The primary immunogenicity objectives are:

- Evaluate the seroconversion rate of S-RBD IgG antibody on Day 28, Day 84 and Week 24 and Week 52 after vaccination, measured by ELISA.
- Evaluate the immunogenicity of one versus two doses of the vaccine.

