### 3. STUDY DESIGN

#### 3.1 Summary

This Phase IIb study is a multi-centre clinical trial; approximately 500 participants 18 years of age and older, living with HIV will be enrolled.

All participants will receive a single dose of the study vaccine (Ad5-nCoV) on First Injection Visit, and a second dose of Ad5-nCoV at Day 56 (Second Injection Visit) and will be followed to monitor vaccine candidate safety, immunogenicity (antibody response), and efficacy for a duration of 52 weeks. A subset of participants will also have cellular immunity measured after receiving the  $5 \times 10^{10}$  vp Ad5-nCoV vaccine ( $\geq 4 \times 10^{10}$  vp).

**Candidate Vaccine:** Ad5-nCoV

**Vaccination schedule:** **A double-dose schedule is used for all participants. The First dose at the Injection Visit when entering the study and the Second dose at Day-56 Visit post baseline vaccination (Second Injection Visit).**

**Data collection:** This clinical trial will use a single, designated Electronic Data Capture System (EDC) where participant electronic case report forms (eCRFs) will be recorded.

**Safety Precautions:** Safety precautions will be outlined in detail in this section, as well as Section 7.

Blinding

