### **3.6 Immunogenicity In-Person Visits**

Participants will return to the study site on Day 28, Day 84, Week 24, and Week 52 for collection of venous blood samples for antibody testing. Approximately 25mL of serum will be collected for ELISA and neutralizing antibody testing on Day 28, Day 84, Week 24, and Week 52.

In the subset of 50 participants, approximately 30mL of whole blood will be collected on Day 28 and Day 84, and Week 24 and Week 52 for ELISpot testing and intracellular cytokine staining (ICS).

*The visit window for immunogenicity participant contact of Day 28 and Day 84 is +/- 7 days.*

*The visit window for immunogenicity participant contact of Week 24 and Week 52 is +/- 14 days.*

*Telephone visits and face-to-face visits at the same time point can be combined into one face-to-face visit.*

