## 9. OUTCOME MEASURES AND STATISTICAL METHODS

### 9.1 Sample Size Estimation

Since this is an open, non-comparative study that seeks to observe the impact of vaccination on the evolution of HIV disease, a sample size defined by statistical criteria is not established.

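### The primary comparison of one versus two doses cannot be delivered: everyone is scheduled for dose 2, and Day 28 is the only planned antibody value after one dose

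*Protocol*

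**What the plan says.** Section 2.1 gives as a primary immunogenicity objective "Evaluate the immunogenicity of one versus two doses of the vaccine". The endpoint list in section 9.3.4 repeats it as "Evaluate the above-mentioned parameters comparing one versus two Ad5-nCoV doses", where the parameters meant are S-RBD IgG seroconversion at Day 28, Day 84, Week 24 and Week 52. The synopsis has the same one-versus-two wording among its primary immunogenicity endpoints, but its objectives list says only "Evaluate the immunogenicity of two doses of the vaccine".

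On dosing, section 3.1 states "A double-dose schedule is used for all participants", with dose 2 at Day 56. Section 1.3 extends this to people enrolled under the former blinded design: "Volunteers initially included in the study will receive two doses of the vaccine". Section 9.1 calls the trial open and non-comparative.

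On sampling, section 3.6 brings participants back "on Day 28, Day 84, Week 24, and Week 52 for collection of venous blood samples for antibody testing". Section 3.2 adds baseline and no other time. The antibody blood-sample rows of Tables 1 and 2 carry no mark under the Day 56 visit.

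On analysis, section 9.3.4 names Fisher's exact test for rates and t-tests for geometric means, both between groups, two-sided at 5%.

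**The concern.** A comparison of one dose with two asks what the second dose adds: the response at a given time after two doses, set against the response that the same people would have had at that time after one. That needs either a one-dose group or, as a weaker substitute, a sample taken just before dose 2. The protocol plans neither.

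What remains is Day 28 against Day 84. The null hypothesis of any test on those values, paired or not, is that the two visits are equal. That differs from the hypothesis that dose 2 adds nothing. If one-dose antibody falls after Day 28, a second dose that only restores the Day 28 level shows as no difference, although it raised antibody from where it stood. If dose 2 did nothing, Day 84 could fall below Day 28 and read as two doses being worse than one. A primary conclusion would then rest on a quantity that does not answer the stated question.

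**Working it through.** The protocol gives no power or sample-size calculation for this comparison; section 9.1 says that no statistical sample size was set. There is no figure to reproduce, so the check is structural, followed by an illustration.

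**1. Samples against doses**

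| Time | Doses received by then | Antibody sample planned |
|---|---|---|
| Day 0 | 0 (before dose 1) | yes |
| Day 28 | 1 | yes |
| Day 56, before dose 2 | 1 | no |
| Day 84 | 2 | yes |
| Week 24 | 2 | yes |
| Week 52 | 2 | yes |

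Day 28 is the only row with one dose and a sample. Day 84 is the matching row, nominally 28 days after dose 2. Weeks 24 and 52 have no one-dose counterpart.

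**2. What the contrast contains**

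Let p84(2) be the seroconversion rate observed at Day 84 after two doses, p84(1) the unobserved rate at Day 84 had only one dose been given, and p28 the rate at Day 28. Then

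p84(2) − p28 = [p84(2) − p84(1)] + [p84(1) − p28].

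The first bracket is the dose-2 effect and the second is change over time. Only the sum is observed. Suppose both visits show 97%, so the contrast is 0. The dose-2 effect is then +17, +7, 0 or −2 percentage points if p84(1) is 80%, 90%, 97% or 99% (97 − 80, 97 − 90, and so on). The same holds for geometric means: an observed Day 84/Day 28 ratio of 1.5 implies a dose-2 ratio of 3.0, 2.0, 1.5 or 1.0 if one-dose titres at Day 84 are 0.5, 0.75, 1.0 or 1.5 times the Day 28 level.

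**3. Illustration for the primary parameter, with no dose-2 effect**

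Inputs from section 1.2 (phase II, healthy adults, the dose used here): 97% seroconversion at Day 28; Day 28 geometric mean 571.0 with interval 467.6 to 697.3, read as a 95% interval. The group size is taken as about 127, from 508 split 2:1:1.

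SD of log10 titre = (log10 697.3 − log10 467.6) / (2 × 1.96) × √127 = 0.1736 / 3.92 × 11.27 = 0.499.

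Assume that log10 fold-rise is normal with this SD and that seroconversion means exceeding a fixed fold-rise. A rate of 97% puts the mean 1.881 SD above the threshold, so the threshold value itself drops out. If titres fall to a fraction f of the Day 28 level, the Day 84 rate is Φ(1.881 + log10 f / 0.499).

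| Assumed decline, Day 28 to 84 | log10 f / 0.499 | Day 84 rate |
|---|---|---|
| 0% | 0 | 97.0% |
| 10% | −0.092 | 96.3% |
| 25% | −0.250 | 94.8% |
| 50% | −0.603 | 89.9% |

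These declines are assumptions. Section 1.2 reports no antibody value after Day 28.

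**4. Would a Day 56 sample isolate the effect?**

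Not fully. Take a paired t-test on log10 titre (a secondary parameter), n = 500, within-person correlation assumed 0.7, no dose-2 effect, and the decline spread log-linearly over Days 28 to 84. The noncentrality is (half the log10 decline) / (0.499 × √(2 × 0.3)) × √500. A Day 56 to Day 84 test then rejects 26% of the time for a 10% decline and 95% for a 25% decline, against a nominal 5%. The sample removes the Day 28 to 56 drift and leaves the rest.

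**The case against.** The strongest reply is that waning is assumed. Section 1.2 says that antibody "peaked at 28 days post vaccination, in all three groups", but gives nothing later. The one account in the protocol of a one-dose course past Day 28 is in section 1.1, for a different adenovirus-vectored vaccine, and there levels lasted to Day 56. This stands. A reader might infer that the comparison will reject because of waning even if dose 2 does nothing. The documents do not support that as fact. With the inputs above (n = 500, SD 0.499, correlation 0.7), a paired t-test of Day 84 against Day 28 with no dose-2 effect rejects 5%, 8%, 25% and 75% of the time for declines of 0%, 2%, 5% and 10%. The answer turns on an unknown. Those figures also concern a secondary parameter and a paired test that the protocol does not name.

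Nor should such rejections be read as a risk of falsely claiming benefit. Under waning the bias runs against dose 2. Intercurrent infection, which can raise S-RBD antibody, would push the other way.

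It can also be said that no Day 28 versus Day 84 test or decision rule is written, and that section 9.1 disclaims comparison. That is fair, but it makes a primary one-versus-two endpoint harder to defend. Participants who miss dose 2 would give later one-dose samples, but they are self-selected and are not named as a comparator.

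Finally, the SAP might settle the method. It could choose a paired analysis. It cannot supply a missing arm or a missing sample.

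**Conclusion.** The point holds as a mismatch between a primary endpoint and the design. Sections 2.1 and 9.3.4 and the synopsis endpoint list promise a comparison that the dosing and sampling schedule cannot provide, and the synopsis objectives list already contradicts them. The dose-2 effect cannot be separated from time at Day 84, and no planned one-dose value exists at Weeks 24 and 52.

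The size is conditional. With a flat one-dose course there is no distortion. With waning the contrast understates dose 2, by about 1, 2 or 7 percentage points of seroconversion for a 10%, 25% or 50% decline (97.0 less 96.3, 94.8 and 89.9). This rests on a 97% Day 28 rate from healthy adults, who may differ from people living with HIV, a normal model with SD 0.499, and no dose-2 effect. A reader might also infer that a Day 84/Day 56 ratio would give the dose-2 effect cleanly. It would not, because it remains a before-after estimate without a concurrent one-dose group.

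**What to change.** In section 2.1, section 9.3.4 and the synopsis endpoint list, replace the one-versus-two wording with the objective already in the synopsis ("Evaluate the immunogenicity of two doses of the vaccine"). Specify that S-RBD seroconversion, with geometric mean titre as secondary, is reported at Day 28 (28 days after dose 1) and Day 84 (nominally 28 days after dose 2) as a within-person difference or ratio with a 95% confidence interval. State that this is a before-after description and not the effect of adding dose 2. Remove the one-versus-two comparison at Weeks 24 and 52, and carry the same wording into the SAP.

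The cost is a few lines of text and a more modest claim. If participants are still to receive dose 2, an antibody sample before the injection at the existing Day 56 visit is optional. It costs one blood draw and assay per person and would remove only the Day 28 to 56 drift, so the before-after caveat must stay.

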#### Secondary Immunogenicity Endpoints:

- GMT of S-RBD IgG antibody on Day 28, Day 84 and Week 24 and Week 52 after vaccination, measured by ELISA.
- GMI of S-RBD IgG antibody on Day 28, Day 84 and Week 24 and Week 52 after vaccination, measured by ELISA.
- Seroconversion rate of pseudo-virus neutralizing antibody on Day 28, Day 84 and Week 24 and Week 52 after vaccination.
- GMT of pseudo-virus neutralizing antibody on Day 28, Day 84 and Week 24 and Week 52 after vaccination.
- GMI of pseudo-virus neutralizing antibody on Day 28, Day 84 and Week 24 and Week 52 after vaccination.
- Positive rate and level of IL-2, IL-4, IL-13, and IFN- $\gamma$  stimulated by peptide pool of S protein on days 28, Day 84 and Week 24 and Week 52 after vaccination, measured by intracellular cytokine staining (ICS).

Geometric mean antibody titers (GMTs) and GMI's and their two side 95% confidence intervals will be calculated by group. Analyses will be performed on the logarithmically (base 10) transformed values. Individual titers below the detection limit will be set to half the limit.

For the analysis of proportions, binomial point estimates and exact binomial confidence intervals will be calculated for each group. Rates will be compared between groups using Fisher's exact tests, and geometric means will be compared using t-tests.

All statistical tests performed for immunogenicity will be 2-sided with Type I error rate of 5%.

Missing values will not be included in the immunogenicity analyses, and there will be no imputation of missing values. No adjustments will be made for multiple comparisons.

Both per-protocol and intent-to-treat immunogenicity analyses will be carried out. The per-protocol immunogenicity analysis set will exclude subjects whose samples were drawn outside of protocol specified time windows.

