  - Participants will donate approximately 25mL of whole blood on First Injection Visit, Day 28, Day 84 and Week 24, and Week 52, as described above. Whole blood will be separated into serum, and then aliquoted. These in-person visits will occur at participants' local study site. A baseline antibody titer against SARS-CoV-2 will be established from the blood sample collected on First Injection Visit, as outlined in the "baseline serology" description. In addition, these samples will also be used to evaluate for additional immunogenicity objectives. Serum collected will be analyzed for the seroconversion rate of S-RBD IgG antibody, GMT of S-RBD IgG antibody, GMI of S-RBD IgG antibody, seroconversion rate of pseudo-virus neutralizing antibody, GMT of pseudo-virus neutralizing antibody, and the GMI of pseudo-virus neutralizing antibody at Day 28, Day 84, Week 24, and Week 52. The second aliquot will be shipped by the central laboratory to Nexelis Laboratories, where it will be stored as a back-up.
  - **Blood collection for ELISpot and ICS measurement**
    - In a subset of approximately 50 participants, approximately 30mL of whole blood will be collected from participants on First Injection Visit, Day 28, Day 84 and Week 24, and Week 52, as described above. TNF, IL-4, IL-5, IL-13 will be measured by ICS on Day 28, Day 84 and Weeks 24 and 52 after vaccination. PBMC will be shipped on dry ice to Nexelis Laboratories (Canada).

- **Final serology**

Participants will have an in-person visit on Month 12. Approximately 25 mL of whole blood will be collected from each participant and separated for serum into two aliquots. The first aliquot will measure antibodies against SARS-CoV-2, at Nexelis laboratories. The second aliquot will be shipped by Nexelis laboratories to the Sponsor, where it will be stored as a back-up. The one-year antibody levels measured against SARS-CoV-2 will be compared to

the participant's baseline levels to evaluate the exploratory efficacy analysis against asymptomatic infection.

*The visit window for immunogenicity in-person visits of Day 28 and Day 84 is +/- 7 days.  
The visit window for immunogenicity in-person visits of Week 24, and Week 52 is +/- 14 days*

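### One versus two doses is a primary comparison, but everyone is planned to receive both doses and the only rate test named is for independent groups

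*Protocol*

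**What the plan says.** Section 2.1 lists as a primary immunogenicity objective: "Evaluate the immunogenicity of one versus two doses of the vaccine". Section 9.3.4 repeats it as a primary endpoint directly after S-RBD IgG seroconversion: "Evaluate the above-mentioned parameters comparing one versus two Ad5-nCoV doses". The synopsis endpoint list agrees, but the synopsis objective reads only "Evaluate the immunogenicity of two doses of the vaccine".

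On design, section 3.1 states "A double-dose schedule is used for all participants". Sections 1.3 and 3.2 extend two doses to those enrolled under the earlier blinded design, including former placebo recipients who continue. Section 9.1 opens with "Since this is an open, non-comparative study".

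On method, section 9.3.4 (and the synopsis in the same words) says "Rates will be compared between groups using" Fisher's "exact tests, and geometric means will be compared using t-tests". Tests are two-sided at 5%. No other comparison method is named for immunogenicity.

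**The concern.** No one-dose arm is planned, and by Week 24 everyone is due to have had both doses. The planned data that bear on one versus two doses are therefore the Day 28 sample (after dose 1) and the Day 84 sample (after dose 2), taken from the same participants. Fisher's exact test treats its two samples as independent. Applied here, it ignores the pairing and uses too large a variance for the difference. The same would hold for the t-test if it were run unpaired.

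The between-group wording fits the former 2:1 placebo design described in section 1.3 and appears to have outlived it. At stake is the ability to show a second-dose gain on a primary endpoint. The per-time-point estimates and exact confidence intervals in 9.3.4 are unaffected.

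**Working it through.** The protocol gives no power figure to reproduce, because section 9.1 sets no statistical sample size. The check is therefore what the named test costs relative to a paired one.

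**Inputs from the protocol.** 500 participants (section 3.2); two-sided 5% (9.3.4); Day 28 S-RBD seroconversion of 97% at this dose in healthy adults (section 1.2).

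**Assumed.** The Day 28 and Day 84 rates in this population and the within-person correlation ρ, varied from 0 to 0.7.

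**Model.** With rates p1 (Day 28) and p2 (Day 84), P(positive at both) = p1·p2 + ρ·√[p1(1−p1)p2(1−p2)].

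For 90% and 94% with ρ = 0.5: 0.846 + 0.5 × √(0.09 × 0.0564) = 0.846 + 0.0356 = 0.8816. Losses are 0.90 − 0.8816 = 0.0184 and gains 0.94 − 0.8816 = 0.0584, about 9 and 29 people in 500.

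**Power for 90% to 94%** (Fisher by simulation on the paired data; exact McNemar on the discordant pairs):

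| Pairs | ρ | Fisher | Exact McNemar |
|---|---|---|---|
| 500 | 0 | 61% | 60% |
| 500 | 0.3 | 63% | 76% |
| 500 | 0.5 | 65% | 89% |
| 500 | 0.7 | 68% | 99% |
| 400 | 0.3 | 51% | 65% |
| 400 | 0.5 | 51% | 79% |
| 400 | 0.7 | 50% | 97% |

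Fisher entries carry simulation error of up to about one point.

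**Other gains, 500 pairs, ρ = 0.5.** From 97% to 99%: 57% against 87%. From 90% to 96%: 99.3% against more than 99.9%.

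**Type I error, 90% at both times, 500 pairs.** Fisher: 1.4%, 0.35% and 0.02% at ρ = 0.3, 0.5 and 0.7, against a nominal 5%. Exact McNemar: 3.8%, 3.5% and 3.0%.

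**One constructed table.** With 455/500 positive at Day 28 and 470/500 at Day 84, from 20 gains and 5 losses, Fisher gives p = 0.092 and exact McNemar p = 0.004.

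**Geometric means, if the t-test were unpaired.** The phase II Day 28 interval in section 1.2 (467.6 to 697.3) and about 127 people (508 split 2:1:1) give SD(log10) = [log10(697.3) − log10(467.6)] / (2 × 1.96) × √127 = 0.499. The unpaired type I error is 2 × [1 − Φ(1.96/√(1−ρ))] = 1.9%, 0.6% and 0.03% at ρ = 0.3, 0.5 and 0.7. Power at ρ = 0.5 with 500 pairs, unpaired against paired: 48% and 78% for an assumed 1.15-fold rise, 94% and 99% for 1.25-fold, about 100% for both at 1.5-fold.

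**Sample timing (secondary).** Section 5.1 says "The visit window for immunogenicity in-person visits of Day 28 and Day 84 is +/- 7 days", and Tables 1 and 2 give Day 56 the same width. If both windows are counted from Day 0, an in-window Day 84 sample can fall from 77 − 63 = 14 to 91 − 49 = 42 days after dose 2, against 21 to 35 days after dose 1.

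**The case against.** The protocol never says that Fisher's test will be applied to Day 28 against Day 84. The groups could be the original randomised allocation, which section 9.2.1 still mentions, or baseline-antibody strata, and Fisher's test would suit either. Section 9.3 leaves details of methods to the SAP. This is a fair caution about intent, but it does not rescue the plan. Neither grouping compares one dose with two, and no other rate test is named, so the primary comparison has either an unsuitable test or none. The correction is the same.

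The cost is also conditional. The error is conservative, no power target or success criterion is attached, and the lead scenario is assumed. If Day 28 seroconversion were near the 97% quoted for healthy adults, at most 3 points could be gained. All of this stands, and it limits the weight of the point.

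The term non-comparative in 9.1 may mean only that there is no comparator arm, so the firmer inconsistency is the synopsis objective. The 14-to-42-day range needs opposite extremes at two visits.

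Finally, pairing does not isolate the second dose: Day 84 against Day 28 also reflects elapsed time and intercurrent infection. Participants who stop after dose 1 would form only an unplanned, self-selected one-dose group. That is a limit on interpretation under any test.

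**Conclusion.** The concern holds and should be fixed. The named rate test does not fit the only planned one-versus-two-dose contrast, and the synopsis objective disagrees with sections 2.1 and 9.3.4 on whether that contrast is planned.

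The consequence is lost power, not false positives. For a 4-point gain with 500 pairs the loss is about 13 to 31 percentage points over correlations of 0.3 to 0.7, and about 24 at 0.5. It disappears at zero correlation and is negligible for large gains. These sizes rest on assumed rates and correlations, since the protocol gives neither for this population. The t-test figures apply only if that test is run unpaired.

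**What to change.** First reconcile the synopsis objective and the non-comparative description in 9.1 with section 2.1, section 9.3.4 and the synopsis endpoint list.

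If the comparison stays, remove the between-group wording for it and state in 9.3.4:

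> One versus two doses is the Day 84 versus Day 28 comparison within participants having both samples. Seroconversion is compared by exact McNemar test with a 95% CI for the paired difference. GMT is compared by paired t-test on log10 titres, reported as the Day 84/Day 28 geometric mean ratio with 95% CI.

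Add a sentence that this contrast also reflects time since enrolment and intercurrent infection. For the per-protocol immunogenicity set, define the post-dose-2 sample by days since the actual second injection.

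The cost is wording in the protocol or SAP, with no new data or visits. Some Day 84 samples may leave the per-protocol set; the protocol does not allow their number to be estimated.
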